## **STUDY PROCEDURES**

**Whole soy pods (soy).** The plants will be grown under carefully monitored conditions at the LSU Agricultural Center and harvested at reproductive stage six or when the green pods contain soybeans that fill the pods. The whole pods will be processed at the United States Department of Agriculture (USDA, New Orleans, LA), Food Processing and Sensory Quality Research Unit, where scientists work with foods for research purposes. Slicing the pods into thin cross-sections injures plant cells and activates the synthesis of an anti-microbial compound (glyceollin) synthesized by the plant *de novo* in response to stress. Glyceollins have been shown to improve insulin sensitivity and cognition. The sliced pods will be lyophilized and milled. Nutrient analysis, will be performed at Eurofins Food Chemistry Testing (Madison, WI) using methods of analysis of the Association of Official Analytical Chemists.

**Food Development.** The soy will be incorporated in foods and prepared by the PBRC metabolic kitchen. The PBRC metabolic kitchen is staffed with research dietitians who have a primary responsibility to develop foods for research purposes, plan diets, and execute their delivery. In addition, the applicant is a registered dietitian with experience in food development across cuisines and cultures.

**Nutrition Counseling.** Subjects will be counseled by the study dietitian who will interview the subject in order to assess the subject's current intake. Based on this information, subjects will be counseled on incorporating the test foods in their diet. We expect that subjects will experience GI symptoms from increased DF intake, but from the applicant's practice as a

registered dietitian and evidence in the literature we know that these symptoms resolve. To enhance compliance with the protocol, subjects will receive counseling on managing GI symptoms.

**Food Tolerability.** Subjects will complete a version of the GI symptoms questionnaire designed as a validated assessment for dyspepsia, and modified to make it specific by only including the symptoms that may be experienced with high DF intake. The scale is ranked as none, mild, moderate, and severe for each of four GI symptoms (bloating, abdominal rumbling, flatulence, and abdominal pain). Additionally, subjects will report their stool frequency ranging from 0 to 9+, and stool consistency based on the Bristol Stool scale.

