## **SAMPLE SIZE AND ANALYSIS**

The primary objective of the study is to determine the maximum tolerated dose of DF. Six subjects at each dose are sufficient to detect tolerability. However, we will enroll 10 subjects to test each dose of DF from soy. Dose safety will be investigated by compiling by treatment (e.g. 4 g dose, 8 g dose, 12 g dose) a list of adverse events such as frequency of headaches, nausea, vomiting. For GI symptoms the scale is ranked as none (no symptoms), mild, moderate, and severe for each of four GI symptoms and the assessment of intensity is provided in the data safety monitoring plan. Moderate and severe ratings will be considered intolerance to the dose. Stool frequency of one to three/day, or three times/ per week is considered regular. Therefore, stool frequency of less than one and more than nine over a 72 hour period will be a consideration for determining intolerance. Stool consistency of Type three to five on the Bristol Stool Scale is considered normal. Any other rating will be considered in the determination of intolerance. To be considered intolerance, subjects must rate stool frequency and consistency as being of moderate to severe intensity.

According to the NCI convention for dose limiting toxicity to a drug, 1) if two out of three (66%) subjects are intolerant to the dose, the next lower dose is the maximum dose tested; and 2) if one out of three (33%) are intolerant to a dose, then that dose is considered the maximum tolerated dose. Therefore for a food, 1) if five out of eight (63%) are intolerant, we will adopt the next lower dose; and 2) if three out of eight (37%) are intolerant to a dose, then that dose will be taken as the maximum tolerated dose.

A mixed effect linear model will be used to estimate changes in the fecal SCFA while accounting for subject correlation across time using all available data. The outcome will be within subject changes over time.

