### Adverse Events

An Adverse Event (AE) is defined as any untoward medical occurrence in a patient or clinical investigation subject, temporally associated with the use of a medicinal product, whether or not considered related to the medicinal product. We define AE as any unfavorable and unintended sign (including a clinically significant abnormal laboratory finding), symptom, or disease (new or exacerbated) temporally associated with the use of the study food.

We will define a serious adverse event (SAE) as any untoward medical occurrence that results in death, is life threatening, requires inpatient hospitalization or prolongation of existing hospitalization, results in persistent or significant disability/incapacity or in a congenital anomaly.

Safety will be assessed by recording all adverse events. The study team will inquire regarding adverse events while minimizing the chance for bias when detecting AEs/SAEs. The study team will employ open-ended and non-leading verbal questioning of the subject as the preferred method to inquire about AE occurrence. For examples, appropriate questions include: "How are you feeling?", "Have you had any (other) medical problems since your last visit/contact?", or "Have you taken any new medicines since your last visit/contact?" It is the responsibility of the investigator to attempt to establish a diagnosis of the event based on signs, symptoms, and/or other clinical information. In such cases, the diagnosis will be documented as the AE/SAE and not the individual signs/symptoms.

**Assessment of Intensity.** An assessment of intensity for each AE and SAE reported during the study will be provided by the investigator and the investigator will assign it to one of the following categories:

Mild: An event that is easily tolerated by the subject, causing minimal discomfort and not interfering with everyday activities.

Moderate: An event that is sufficiently discomforting to interfere with normal everyday activities.

Severe: An event that prevents normal everyday activities.

An AE that is assessed as severe will not be confused with an SAE and both AEs and SAEs can be assessed as severe. Severe Adverse Event is a category utilized for rating the intensity of an event.

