## 2.0 INTERIM ANALYSIS

The primary objective of the study is to determine the maximum tolerated dose of dietary fiber. Dose safety will be investigated by compiling by treatment (e.g. 4 g dose, 8 g dose, 12 g dose) a list of adverse events such as frequency of headaches, nausea, vomiting. For GI symptoms the scale is ranked as none (no symptoms), mild, moderate, and severe for each of four GI symptoms and the assessment of intensity is provided in the section on adverse events.

Moderate and severe ratings will be considered intolerance to the dose. Stool frequency of one to three/day, or three times/per week is considered regular. Therefore, stool frequency of less than one and more than nine over a 72-hour period will be a consideration for determining intolerance. Stool consistency of Type three to five on the Bristol Stool Scale is considered normal. Any other rating will be considered in the determination of intolerance. To be considered intolerance, subjects must rate stool frequency and consistency as being of moderate to severe intensity. If a dose is tolerated, subjects will receive the next escalated dose for one week.

**Stopping Rules.** The study foods will be stopped, and further dosing will be halted until un-blinded safety information can be reviewed in the event that:

- A death occurs.
- Two or more subjects experience the same SAE following administration of study product.
- Based on AEs, laboratory findings, or clinical findings the Investigator determines that review of pertinent safety information is required.

Dosing may only resume if, after review of safety information, both the Investigator and IRB agree that it is safe to proceed.

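### The intolerance count behind the maximum tolerated dose is defined from four questionnaire symptoms and stool items; moderate or severe adverse events outside that scale are not stated to count

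*Combined protocol and SAP*

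**What the plan says.** **The scale.** Food Tolerability, under STUDY PROCEDURES, describes a questionnaire cut down to fibre-related symptoms: "The scale is ranked as none, mild, moderate, and severe for each of four GI symptoms (bloating, abdominal rumbling, flatulence, and abdominal pain"). Stool frequency and consistency are reported as well. Nausea, vomiting and headache are not on it.

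**The intolerance criteria.** SAMPLE SIZE AND ANALYSIS puts dose safety first, as a by-dose compilation of "a list of adverse events such as frequency of headaches, nausea, vomiting". It then turns to the four-symptom scale and states: "Moderate and severe ratings will be considered intolerance to the dose". The stool criterion follows: "To be considered intolerance, subjects must rate stool frequency and consistency as being of moderate to severe intensity". Section 2.0 INTERIM ANALYSIS of the data safety monitoring plan repeats this text and adds that, for the GI symptom scale, "the assessment of intensity is provided in the section on adverse events".

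**The decision rule.** The primary conclusion depends on the number of intolerant subjects: "if five out of eight (63%) are intolerant, we will adopt the next lower dose". If three of eight are intolerant, that dose is the maximum tolerated dose.

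**What is recorded on adverse events.** Section 1.2 provides that "An assessment of intensity for each AE and SAE reported during the study will be provided by the investigator", graded mild, moderate or severe, and it requires a causality judgement for each event. Adverse events are assessed in the same telephone call as the questionnaire, the day before the visit (Visit 1 to Visit 3). They can lead to withdrawal (section 1.3), can halt dosing (section 2.0, Stopping Rules), and may enter the discussion of escalation between the principal investigator and the Safety Officer (section 3.2).

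**The concern.** The primary result is a count of intolerant subjects, so the definition of an intolerant subject is the endpoint. The plan states that its rule is adapted from the convention for dose-limiting toxicity, and it names nausea and vomiting as examples of adverse events to compile. Yet neither appears in the criteria that make a subject intolerant. Applied literally, the rule would count a subject with severe, food-related vomiting and only mild ratings on the four symptoms as tolerant. A subject withdrawn during a dose week may have no end-of-week rating, and no sentence says how that subject is classified.

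The possible error runs one way. Adding a class of intolerant subjects can raise the count or leave it unchanged, so omitting the class can only favour calling a dose tolerated. With eight subjects, one person separates 3/8 from 2/8 and 5/8 from 4/8. The dose chosen here is meant to inform a later efficacy trial.

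**Working it through.** **1. The plan's own figures.** 5/8 = 62.5% (stated as 63%) and 3/8 = 37.5% (stated as 37%). Both reproduce apart from rounding. The sample size rests on cited precedent, with no assumed intolerance rate, so nothing in the documents fixes how often the omission would occur.

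**2. What feeds the count.**

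| Item | Where | Tied to the 3/8 and 5/8 count? |
|---|---|---|
| Four symptoms rated moderate or severe | Sample Size and Analysis; 2.0 | Yes |
| Stool frequency and consistency | Sample Size and Analysis; 2.0 | Yes |
| Headache, nausea, vomiting | Sample Size and Analysis; 2.0 | Listed by dose; not stated to count |
| Intensity and causality of each event | 1.2 | Recorded; not stated to count |
| Withdrawal for an adverse event | 1.3 | Not stated |
| Halting of dosing | 2.0, Stopping Rules | Not stated |
| Discussion of escalation | 3.2 | Not stated |

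**3. Illustration of size.** Inputs: n = 8, as the rule is written. The cut-offs are read as at least 3 and at least 5. Two rates must be assumed:

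- q: the chance that a subject meets the written questionnaire or stool criterion.
- a: the chance of a moderate or severe adverse event outside the scale in a subject who does not meet that criterion.

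With such events counted, the chance of intolerance is p = q + (1 − q)a. The number intolerant is taken as binomial(8, p), with subjects independent.

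For q = 0.20 and a = 0, p = 0.20:
P(at least 3) = 1 − [0.8⁸ + 8(0.2)(0.8⁷) + 28(0.2²)(0.8⁶)] = 1 − [0.1678 + 0.3355 + 0.2936] = 0.203.

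For q = 0.20 and a = 0.10, p = 0.20 + 0.80 × 0.10 = 0.28:
P(at least 3) = 1 − [0.72⁸ + 8(0.28)(0.72⁷) + 28(0.28²)(0.72⁶)] = 1 − [0.0722 + 0.2247 + 0.3058] = 0.397.

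The other entries use the same formula:

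| q | a | p | P(at least 3 of 8) | P(at least 5 of 8) |
|---|---|---|---|---|
| 0.20 | 0 | 0.200 | 0.203 | 0.010 |
| 0.20 | 0.05 | 0.240 | 0.297 | 0.023 |
| 0.20 | 0.10 | 0.280 | 0.397 | 0.044 |
| 0.20 | 0.20 | 0.360 | 0.596 | 0.118 |
| 0.30 | 0 | 0.300 | 0.448 | 0.058 |
| 0.30 | 0.05 | 0.335 | 0.536 | 0.090 |
| 0.30 | 0.10 | 0.370 | 0.619 | 0.131 |
| 0.30 | 0.20 | 0.440 | 0.762 | 0.242 |

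**4. Chance that the omission itself crosses a cut-off.** Every subject intolerant on the questionnaire rule is also intolerant on the wider one. The difference between rows is therefore the chance that the omission alone takes the count below the cut-off. At q = 0.20 and a = 0.10 this is 0.397 − 0.203 = 0.194 for the cut-off of three, and 0.0438 − 0.0104 = 0.033 for the cut-off of five.

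**5. Denominator.** The rule is written for eight, but 10 are to be enrolled. If three of eight is carried over as four of 10 (0.375 × 10 = 3.75, rounded up), the same assumed rates give P(at least 4 of 10) = 0.121 without and 0.298 with these events. The direction is the same.

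**The case against.** The strongest reply is that no sentence excludes adverse events from intolerance. Just before saying that moderate and severe ratings mean intolerance, the plan sends the reader to the adverse event intensity grades, so the word for ratings could be taken to cover adverse events too. That reading is open but strained: the pointer belongs to a sentence about the GI symptom scale, and what it supplies is the meaning of the grades for those four symptoms. If both readings are allowed, the primary endpoint is ambiguous, which also needs repair.

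A second reply is that adverse events do affect the trial, through withdrawal, the stopping rules and the Safety Officer discussion. This is true, and it means a reader should not infer that such events are merely listed or can have no effect on dosing. But these routes are largely matters of judgement. The fixed triggers in the stopping rules are a death, or the same serious event in two or more subjects, and severe vomiting need not be serious as the plan defines it. None of the routes changes a subject's status in the count.

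Third, the separation may be deliberate: the questionnaire was narrowed to fibre symptoms and the drug convention was adapted for a food. A fibre-specific endpoint with adverse events reported beside it is defensible if it is stated as the choice.

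Three stronger inferences are not supported. The plan gives nausea and vomiting as examples and does not call them expected. It does not say that a withdrawn subject counts as tolerant; it is silent. And an assumed 10% rate of such events gives 1 − 0.9⁸ = 0.570 as the chance that at least one of eight subjects has one. That is not the chance of a changed conclusion, which requires the count to sit near a cut-off.

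**Conclusion.** The concern holds in a limited form. On the natural reading, the count that names the maximum tolerated dose takes in only the four symptoms and the stool items. Moderate or severe adverse events outside the scale, and withdrawal for one, are not stated to count. Under that reading the omission can only favour calling a dose tolerated.

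Its size cannot be established from the documents. With an assumed 20% meeting the written criterion, and 5%, 10% or 20% of the rest having such an event, the chance of reaching three of eight rises from 0.203 to 0.297, 0.397 or 0.596. At 10%, the chance of reaching five of eight rises from 0.010 to 0.044. These figures assume independent subjects and eight evaluable at the dose. If such events are rare the effect is small, but the classification should still be settled before any subject is counted.

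**What to change.** Reconcile SAMPLE SIZE AND ANALYSIS with sections 1.2, 1.3, 2.0 and 3.2 of the data safety monitoring plan on whether an adverse event outside the questionnaire counts as intolerance in the primary analysis.

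For the maximum tolerated dose, report two numbers at each dose:

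1. Subjects intolerant on the questionnaire and stool rule alone.
2. Subjects intolerant on that rule, plus those with a moderate or severe adverse event judged related to the study food in that dose week, or withdrawn for one.

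State before enrolment which number determines the conclusion. The other then serves as a sensitivity display.

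The cost is a sentence or two and one extra row in a table. Intensity, causality and the week of occurrence are already recorded, so no new data are needed. The drawback is that the investigator's causality judgement, in a study without masking (section 3.3), enters the second number; showing both makes its influence visible.

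This change concerns only how the primary count is classified and reported. Tolerating a dose also decides whether a subject receives the next one. Whether such events govern that step is for the sponsor to reconcile, and no rule is proposed here.

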#### **CLINIC VISITS**

Subjects will complete one screening visit. There will be four study visits **unless a participant is intolerant to a dose and cannot be advanced to the next higher dose.**

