### **Baseline (1 hour)**

Subjects will report to the clinic for the visit. The following tests and measurements will be performed:

- Collection of fecal sample.
- Measurement of weight and vital signs.
- Recording of medications.
- Dispensation of study foods.
- Nutrition counseling.
- Completion of tolerability questionnaire.
- Dispensation of stool collection kit.

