### 3.2 Data Analysis and Coordination

The proposed safety officer is a physician in the PBRC Outpatient Clinic. The safety officer is independent of the study. The PI will discuss tolerability with the Safety Officer during the dose titration to determine whether the next escalation of dose is indicated. All of the data except raw data identifying individual participants will be made available to the Safety Officer and upon request to the Program Officer.

At the end of the study, a manuscript will be prepared for submission to a peer-reviewed journal. A summary of the results will be posted on ClinicalTrials.gov which subjects may access.

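### The MTD count uses absolute GI ratings and gives no role to the subject's own baseline rating, so unchanged pre-existing symptoms count as intolerance to soy

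*Combined protocol and SAP*

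**What the plan says.** Under Food Tolerability, each of four symptoms (bloating, rumbling, flatulence, abdominal pain) is rated none, mild, moderate or severe. Sample Size and Analysis turns the ratings into a yes/no outcome: "Moderate and severe ratings will be considered intolerance to the dose". Section 2.0 Interim Analysis of the data safety monitoring plan repeats the sentence. The outcome feeds two limits. At the lower one, "if three out of eight (37%) are intolerant to a dose, then that dose will be taken as the maximum tolerated dose". At the upper one, five of eight, the next lower dose is adopted.

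The questionnaire is also completed before dosing. Table 1 marks it at baseline, and the Baseline visit lists "Completion of tolerability questionnaire" alongside the first dispensing of study foods. No section says how that rating enters the count. Section 3.3 of the monitoring plan states that every subject receives the study product, so there is no control group.

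Three other provisions come close to a baseline or causality comparison:

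- An adverse event includes any unfavourable "symptom, or disease (new or exacerbated) temporally associated with the use of the study food", and pre-existing conditions that have not worsened are left out.
- The investigator assesses the relation of each adverse event to study treatment (Assessment of Causality).
- Section 3.2 says: "The PI will discuss tolerability with the Safety Officer during the dose titration to determine whether the next escalation of dose is indicated".

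**The concern.** A count meant to measure intolerance to a dose of soy should not include symptoms that the subject had at the same level before eating any. Under the rule as written it does, and with no control group only the baseline questionnaire tells the two apart within the study.

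The MTD is the primary objective and is meant to inform the later efficacy trial. The limits are small counts, so one or two subjects with long-standing symptoms can decide the result. The same subjects move through successive doses, so a persistent symptom is already present at the first dose. At 4 g or 8 g, reaching three of eight fixes the MTD there. At 12 g, the top dose, reaching three of eight lowers nothing.

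**Working it through.** **Inputs from the documents.** Limits of three and five out of eight (Sample Size and Analysis); 10 subjects enrolled (Study Subjects; Sample Size and Analysis); the absolute definition quoted above.

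**Inputs assumed.** The background rate b is the share of subjects whose moderate or severe rating was present at baseline and is unchanged on soy. The documents give no value, so 5% to 30% is shown. The soy effect is set to zero, subjects are treated as independent, and the limits are read as three or more and five or more.

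**The plan's own figures.** 5/8 = 62.5%, printed as 63%. 3/8 = 37.5%, printed as 37%. Both reproduce apart from rounding. The plan states no error rate or power to reproduce.

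**A case that needs no rate.** If three of eight subjects have an unchanged moderate symptom, the count at 4 g is 3/8 and 4 g becomes the MTD, although soy has done nothing.

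**Chance of crossing a limit at one dose.** With n subjects assessed,

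P(X ≥ k) = 1 − Σ C(n,x) bˣ (1−b)ⁿ⁻ˣ, summed over x = 0 to k−1.

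For n = 8 and k = 3:

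- b = 5%: 1 − (0.6634 + 0.2793 + 0.0515) = 0.0058
- b = 20%: 1 − (0.1678 + 0.3355 + 0.2936) = 0.2031

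| Background b (assumed) | P(3 or more of 8) | P(5 or more of 8) |
|---|---|---|
| 5% | 0.006 | < 0.001 |
| 10% | 0.038 | 0.0004 |
| 20% | 0.203 | 0.010 |
| 30% | 0.448 | 0.058 |

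**Dependence on the denominator.** The limits are written for eight, but 10 are enrolled. At b = 20% with 10 assessed:

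- Limit kept at three: 1 − (0.1074 + 0.2684 + 0.3020) = 0.322.
- Limit scaled: 37.5% of 10 is 3.75, so four subjects. Subtracting the term for x = 3 gives 0.3222 − 0.2013 = 0.121.

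The value at 20% background is therefore 0.12, 0.20 or 0.32, depending on a point that the plan leaves open.

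**After the change.** If a rating counts only when it is moderate or severe and also worse than that subject's baseline, an unchanged symptom contributes nothing. With no soy effect and stable symptoms, both probabilities are zero at every b.

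**Do the other provisions close the gap?** Section 2.0 refers to the adverse-event section for one thing: "the assessment of intensity is provided in the section on adverse events". Sample Size and Analysis refers to the monitoring plan in the same limited way. What is borrowed is the meaning of mild, moderate and severe. The exclusion of unworsened conditions and the causality step belong to adverse events and are not tied to the three-of-eight or five-of-eight counts. The Safety Officer discussion concerns escalation and gives no counting rule.

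**The case against.** The strongest reply is that the gap is narrower than it looks. The intensity categories are defined for adverse events, adverse events must be new or worsened, and intolerance to a dose is attributive wording. A reader might infer that unchanged symptoms are already left out. The documents do not support that: the cross-reference covers intensity only, and Food Tolerability describes ratings made by the subject, whereas adverse-event intensity is assigned by the investigator. What stands is that the investigators may well intend a baseline comparison. If so, it rests on unwritten judgment in an unmasked study.

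The second reply is about size, and it largely stands. Subjects are described as healthy, malabsorption syndromes such as chronic diarrhoea are excluded, and moderate means "An event that is sufficiently discomforting to interfere with normal everyday activities". Background rates of 20% to 30% may be too high, and at 5% the effect is negligible. Against this, the exclusions do not name bloating, rumbling, flatulence or abdominal pain.

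The third reply is that an absolute rating is a defensible measure of total symptom burden on the dose. That is fair, and is a reason to keep the absolute count on display. It does not justify reading that count as intolerance caused by the dose.

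**Conclusion.** The point holds. As written, the MTD count includes unchanged pre-existing moderate or severe symptoms, and nothing else in the documents takes them out. At the dose where this happens the count is inflated, and 4 g or 8 g can become the MTD without a soy effect. The size is uncertain: negligible at 5% background, small at 10%, and material for the three-of-eight limit at 20% or more. For the five-of-eight limit it stays at or below 0.06 with eight assessed. All of this rests on assumed background rates and on the eight-versus-10 question.

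Two stronger readings should be resisted. A reader might take the probabilities as the chance of a wrong MTD, but they are chances of crossing a limit at one dose. A reader might also infer that the final MTD must be biased downward. The documents do not fix the net direction over the whole escalation, because they do not say how subjects who are not advanced enter the counts at higher doses. That is a separate issue, and the change below does not settle it.

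**What to change.** In the MTD analysis of Sample Size and Analysis:

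- Count a symptom rating as intolerance when it is moderate or severe and worse than the same subject's baseline rating for that symptom.
- At each dose, report the absolute-rating count and the baseline ratings beside this count.
- List subjects already severe at baseline, who cannot score as worse.

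Sample Size and Analysis and section 2.0 must then be reconciled. In section 2.0 the same definition leads directly to the next dose, and Clinic Visits plans all study visits "unless a participant is intolerant to a dose and cannot be advanced to the next higher dose". Each section should say which definition serves the MTD count and which serves individual advancement. The advancement criterion is for the investigators, and none is proposed here.

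The cost is small: a changed definition, one added display, and no new data, since the baseline questionnaire is already scheduled. There are two downsides. A single baseline reading on a four-level scale is noisy, and subjects severe at baseline cannot register worsening. Showing both counts and listing those subjects keeps both limitations visible.

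### Stool changes count as intolerance only with a subject intensity rating that the questionnaire, as described, does not collect

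*Combined protocol and SAP*

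**What the plan says.** **Instrument.** Study Procedures (Food Tolerability) describes the questionnaire in two parts. On symptoms: "The scale is ranked as none, mild, moderate, and severe for each of four GI symptoms"; the four named are abdominal pain, bloating, flatulence and rumbling. On stool: "Additionally, subjects will report their stool frequency ranging from 0 to 9+, and stool consistency based on the Bristol Stool scale". No recall period is given for the count.

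**Rule.** Sample Size and Analysis treats a moderate or severe rating on the four symptoms as intolerance. For stool it first defines normal ("Stool frequency of one to three/day, or three times/ per week is considered regular", and Bristol types 3 to 5). It then says that "stool frequency of less than one and more than nine over a 72 hour period will be a consideration for determining intolerance", and that any other Bristol type is also considered. It closes with the condition "To be considered intolerance, subjects must rate stool frequency and consistency as being of moderate to severe intensity". Section 2.0 (Interim Analysis) of the monitoring plan repeats that condition.

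**Use.** Sample Size and Analysis sets the maximum tolerated dose from the number intolerant: at five of eight the next lower dose is adopted, and at three of eight the current dose is the maximum. Clinic Visits and section 2.0 make each subject's move to the next dose depend on tolerating the current one.

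**The concern.** The rule needs a response that the described instrument does not ask for. A count and a Bristol type describe what happened; neither records how intense the subject found it. If the form matches its description, a subject with troublesome constipation or diarrhoea, but nothing above mild on the four symptoms, can never satisfy the stool condition.

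Two things are at stake:

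- **The primary outcome.** The tally that sets the maximum tolerated dose can understate intolerance.
- **The subject.** Someone intolerant on stool alone would be classed as tolerant and moved to the next dose.

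If staff instead supply a rating case by case, the direction of any error is unknown and the primary outcome rests on an unwritten rule.

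**Working it through.** **Step 1. Does any passage supply the missing rating?**

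- *Questionnaire description.* Intensity applies to four named symptoms. Stool is reported in a separate sentence, as a count and a type.
- *Cross-reference to intensity definitions.* In section 2.0 it reads "for each of four GI symptoms and the assessment of intensity is provided in the section on adverse events". It belongs to the sentence on the four symptoms, not to stool. Sample Size and Analysis has the same structure.
- *Definitions it leads to.* Section 1.2 (Assessment of Intensity): "An assessment of intensity for each AE and SAE reported during the study will be provided by the investigator". The rater is the investigator and the object is an adverse event. The rule asks for a rating by the subject, of stool frequency and consistency.
- *Safety Officer.* Section 3.2: "The PI will discuss tolerability with the Safety Officer during the dose titration to determine whether the next escalation of dose is indicated". This is a discussion, with no grading rule for stool.

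None of these supplies the subject rating.

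**Step 2. Can the recorded count stand in for it?** The limits are fewer than one and more than nine stools in 72 hours. The recall window is not stated, so three are assumed in turn.

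- *24 hours.* A subject with three stools a week is regular by the plan's definition and has at least 7 − 3 = 4 days at zero. A report of 0 therefore does not show fewer than one in 72 hours.
- *72 hours.* Three a day is 3 × 3 = 9, which is regular. If 9+ means nine or more, it pools this with the flagged range. If 9+ means more than nine, both limits can be read exactly.
- *7 days.* One to three a day is 7 to 21 a week. At a constant daily rate, the upper limit corresponds to more than 9 × 7/3 = 21 a week. The category 9+ then holds both regular and flagged subjects. Without a constant rate the weekly total does not translate to 72 hours at all: ten stools in three days and one a day for four days gives 10 + 4 = 14.

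Whether the count can be read against the limits thus depends on two unstated definitions, the window and the top category. In any case the plan makes the count only one consideration, so this is secondary to Step 1.

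**Step 3. Effect of one uncounted stool-only subject.** The plan's fractions are 5/8 = 62.5% (stated as 63%) and 3/8 = 37.5% (stated as 37%). One subject is 1/8 = 12.5 percentage points. Assume eight evaluable subjects and read the thresholds as 'or more':

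- *Four others counted.* 4/8 = 50% instead of 5/8 = 62.5%. The dose is kept as the maximum instead of the next lower one being adopted.
- *Two others counted, below 12 g.* 2/8 = 25% instead of 3/8 = 37.5%. Escalation goes on instead of stopping at that dose.
- *Two others counted, at 12 g.* There is no higher dose, so 12 g remains the maximum either way.
- *Any other number counted.* The tally result does not change, but that subject's own advancement still does.

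**Step 4. Denominator.** Study Subjects and Sample Size and Analysis also state 10 enrolled, and the rule is not restated for 10. Subjects who do not tolerate a dose are not advanced, so fewer may reach 8 g and 12 g. The comparisons in Step 3 therefore hold only where eight subjects are evaluable at the dose in question.

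**The case against.** **This is silence, not contradiction.** Study Procedures summarises a form that is not reproduced, and it never says that the severity scale excludes stool. Since the rule says that subjects must rate stool, the form may well carry the item. This stands as a limit: a reader might infer that the questionnaire lacks the rating, but the documents show only that its description does.

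**The information is not wholly lost.** An unfavourable bowel change can qualify as an adverse event. Adverse events are assessed on the same phone call as the questionnaire, graded by interference with everyday activities and compiled by dose. This stands in part. A contemporaneous grade may exist for events reported that way, so it would be too strong to say that nothing could be recovered. It is still the investigator's grade, and the written rule does not use it for stool.

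**The count may be usable.** The ends of the scale, 0 and 9+, resemble the 72-hour limits. With a 72-hour window and 9+ meaning more than nine, both limits are readable. This also stands. A reader might infer that the count fails under every recall window; the documents do not establish that.

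**No effect is shown.** The documents give no rate of stool-only intolerance, and the result shifts only at a boundary. This is correct, and no rate is assumed here. It limits the size of the point but does not reconcile the instrument with the rule.

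**Conclusion.** The point holds for the instrument as described. The plan makes a subject intensity rating a condition for counting stool changes, and no passage says that such a rating is collected. A subject whose only problem is stool then cannot be counted under the written rule. Intolerance can be understated in the tally for the primary outcome, and that subject's advancement is affected.

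The size is unknown. With eight evaluable subjects and thresholds read as 'or more', one missed case changes the result at 4 versus 5 of 8, or at 2 versus 3 of 8 below 12 g, and at no other count. A subject who also rates one of the four symptoms moderate or severe is counted anyway.

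A reader might go further and infer that the maximum tolerated dose will come out too high. The documents do not support that: the form may hold the item, staff may supply a rating case by case, and the tally may lie away from a boundary. The matter should be settled before enrolment, because it concerns the definition of the primary outcome and is cheap to correct. Confidence is medium, mainly because the form cannot be seen.

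**What to change.** Before enrolment, reconcile Food Tolerability with Sample Size and Analysis and with section 2.0, by one of two routes:

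1. Add a subject intensity rating for stool frequency and for stool consistency to the existing questionnaire, at baseline and at each weekly call, and describe it. If the form already has these items, describe them.
2. State how the recorded count and Bristol type are converted to intolerance, and by whom.

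Under either route:

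- State whether frequency and consistency must both qualify or whether one is enough.
- Set the recall window of the count to match the 72-hour limit.
- Define the top category so that nine and more than nine can be told apart.

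Any clinical threshold is for the sponsor to set.

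**Cost.** At most two items in a questionnaire already scheduled at baseline and before each later visit, plus wording. If the form already holds the rating, or the second route is chosen, only wording is needed, apart from any change to the count's window or top category. No visit or staff is added.
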